10.4.3 Serious Adverse Events requiring expedited reporting to the Trial Office

All SAEs not listed in Sections 10.4.1 and 10.4.2 10.4.1 Error! Reference source not found. must be reported to the Trial Office on a trial specific SAE form within 24 hours of the site research team becoming aware of the event.

10.5 SAE Reporting process

On becoming aware that a participant has experienced an SAE which requires reporting, the PI or delegate should report the SAE to their own Trust in accordance with local practice and to the Trial Office as per the guidance in section 10.4.

To report an SAE to BCTU, the PI or delegate must complete, date and sign an SAE form via the STABILISE trial EDC system using the process described below in the timeline specified in sections 10.4.2 and any other relevant anonymised documents should be submitted to BCTU via the STABILISE trial mailbox ([contact]) to make BCTU aware that an SAE has been submitted, along with any other relevant anonymised documentation.

To report an SAE, submit the SAE Form to via the trial EDC system

Where an SAE form has been completed by someone other than the PI (or medically qualified delegate) initially, the PI must review and record confirmation of agreement with the causality and severity assessments on the SAE form.

SAEs will be recorded directly in the trial EDC system (on a single form per event) which can be edited to add additional information. On receipt of an SAE form, the trial Office at BCTU will allocate each SAE a unique reference number and notify the site via email as a proof of receipt. The site and the Trial Office should ensure that the SAE reference number is quoted on all correspondence and follow-up reports regarding the SAE and filed with the SAE in the ISF.

Site should also email the trial mailbox to inform BCTU that they have submitted an SAE. If the site has not received confirmation of receipt of the SAE within 1 working day of reporting, the site should contact the Trial Office.

Copies of the completed SAE form should be printed on resolution of the SAE and filed in the ISF.

10.5.1 Assessment of causality of an SAE

When completing the SAE form, the PI (or, throughout this section, a medically qualified delegate) will be asked to define the nature of the seriousness and causality (relatedness; see Table 4: Categories of causality) of the event. In defining the causality, the PI must consider if any concomitant events or medications may have contributed to the event and, where this is so, these events or medications should be reported on the SAE form.

As per Table 4: Categories of causality, all events considered to be 'possibly', 'probably', or 'definitely' related to the intervention will be reported by the trial office as 'related'; all events considered at site to be 'unlikely' or 'unrelated' to the intervention will be reported by the trial's office as 'unrelated'. The same categorisation should be used when describing AEs and protocol-exempt SAEs in the source data.

Category	Definition	Causality	
Definitely	There is clear evidence to suggest a causal relationship, and other possible contributing factors can be ruled out.		
Probably	There is evidence to suggest a causal relationship, and the influence of other factors is unlikely.	Related	
Possibly	There is some evidence to suggest a causal relationship. However, the influence of other factors may have contributed to the event (e.g., the participant's clinical condition, other concomitant events or medication)		
Unlikely	There is little evidence to suggest there is a causal relationship. There is another reasonable explanation for the event (e.g., the participant's clinical condition, other concomitant events or medication).	Unrelated	
Not related	There is no evidence of any causal relationship.		

Table 4: Categories of causality

On completion of an SAE Form, the Trial Office will contact the Chief Investigator (CI) or delegate(s) and ask them to access the electronic SAE form and independently* review the causality of the SAE.

An SAE judged by the PI or CI or delegate(s) to have a reasonable causal relationship ("Related" as per Table 4: Categories of causality) with the intervention will be regarded as a related SAE (i.e., SAR). The severity and causality assessment given by the PI will not be downgraded by the CI or delegate(s). If the CI or delegate(s) disagrees with the PI's causality assessment, the opinion of both parties will be documented, and where the event requires further reporting, the opinion will be provided with the report.

*Where the CI is also the reporting PI an independent clinical causality review will be performed.

10.5.2 Assessment of expectedness of an SAE by the CI

The CI or delegate(s) will also assess all related SAEs for expectedness with reference to the criteria in Table 5: Categories of expectedness.

Category	Definition
Expected	An adverse event that is consistent with known information about the trial related procedures or that is clearly defined in the relevant safety information (SmPC)
Unexpected	An adverse event that is not consistent with known information about the trial related procedures.

 Table 5: Categories of expectedness

If the event is unexpected (i.e., it is not defined in the approved version of the reference safety information (RSI) it will be classified as a Suspected Unexpected Serious Adverse Reaction (SUSAR). The CI will undertake review of all SAEs and may request further information from the clinical team at site for any given event(s) to assist in this.

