10. ADVERSE EVENT REPORTING

10.1 Definitions

Table 3: Adverse event reporting definitions

Severity Definitions	Mild Moderate Severe	Awareness of signs or symptoms that do not interfere with the participant's usual activity or are transient and resolved without treatment and with no sequelae. A sign or symptom, which interferes with the participant's usual activity. Incapacity with inability to do work or perform usual activities.
Adverse Event	AE	Any untoward medical occurrence in a participant administered a medicinal product and which does not necessarily have a causal relationship with this intervention. An AE can therefore be any unfavourable and unintended sign (including abnormal laboratory findings), symptom or disease temporally associated with the use of an investigational medicinal product, whether or not related to the investigational medicinal product.
Adverse Reaction	AR	All untoward and unintended responses to an IMP related to any dose administered. An AE judged by either the reporting Investigator or Sponsor as having causal relationship to the IMP qualifies as an AR. The expression reasonable causal relationship means to convey in general that there is evidence or argument to suggest a causal relationship.
Serious Adverse Event	SAE	Any untoward medical occurrence or effect that: Results in death Is life-threatening* Requires hospitalisation or prolongation of existing hospitalisation Results in persistent or significant disability or incapacity Is a congenital anomaly/birth defect Or is otherwise considered medically significant by the Investigator**
Serious Adverse Reaction	SAR	An AR which also meets the definition of a SAE.
Unexpected Adverse Reaction	UAR	An AR, the nature or severity of which is not consistent with the applicable product information (e.g., Investigator Brochure for an unapproved IMP or (compendium of) Summary of Product Characteristics (SPC) for a licensed product).

		When the outcome of an AR is not consistent with the applicable product information the AR should be considered unexpected.
Suspected Unexpected Serious	SUSAR	A SAR that is unexpected i.e., the nature, or severity of
Adverse Reaction		the event is not consistent with the applicable product information. A SUSAR should meet the definition of an AR, UAR and SAR.

* The term life-threatening is defined as diseases or conditions where the likelihood of death is high unless the course of the disease is interrupted.

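### Table 5's test of expectedness conflicts with the sentence below it and with Table 3, so a serious vaccine reaction could be classed as expected and miss expedited SUSAR reporting

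*Protocol*

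**What the plan says.** Protocol section 10.5.2 says the chief investigator or delegate "will also assess all related SAEs for expectedness with reference to the criteria in Table 5: Categories of expectedness". Table 5 has two rows.

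- The Expected row reads: "An adverse event that is consistent with known information about the trial related procedures or that is clearly defined in the relevant safety information (SmPC").
- The second row, Unexpected, covers an event that is not "consistent with known information about the trial related procedures". This row does not mention the SmPC.

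The sentence directly below the table gives the SUSAR trigger: the event is unexpected, and so a SUSAR, if "it is not defined in the approved version of the reference safety information (RSI").

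Table 3 in section 10.1 defines an unexpected adverse reaction as "An AR, the nature or severity of which is not consistent with the applicable product information". It adds that a reaction whose outcome does not match the product information is also unexpected. On SUSARs it says: "A SUSAR should meet the definition of an AR, UAR and SAR".

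Section 10.5.1 limits which events reach this step. Only an SAE judged to have a reasonable causal relationship "with the intervention will be regarded as a related SAE (i.e., SAR") is assessed for expectedness.

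Section 10.6 sets the reporting clocks. Fatal or life-threatening SUSARs go to the MHRA, REC and the sponsor's research governance team within 7 days, and other SUSARs within 15 days. All SARs, SUSARs included, are listed in the annual Development Safety Update Report (DSUR).

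**The concern.** For an SAE already judged related to the vaccine, expectedness is the last decision separating expedited reporting from annual reporting. The protocol words that decision differently in three places, and the one named as the criteria, Table 5, is the loosest.

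The reference to trial procedures does not fit the purpose. A SAR is tied to the intervention, and Table 3 judges its expectedness against product information only. Because the vaccine is given by intradermal injection, the line between a reaction to the product and an event of the procedure is easily blurred.

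At stake is timely notice to the regulator, the ethics committee and the site investigators of an unlisted or unusually severe serious reaction to a live attenuated vaccine.

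**Working it through.** The protocol gives no figure on this point, so the check sets the rules side by side and runs each type of event through them. Every event considered is serious and already judged related to the vaccine. P means it is consistent with what is known of the trial procedures; S means the reaction appears in the SmPC. For the comparison, the SmPC, the applicable product information and the approved RSI are assumed to have the same content; the protocol uses all three terms.

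| Event | Table 5 | Sentence below Table 5 | Table 3 |
|---|---|---|---|
| 1. P yes, S yes, severity and outcome as listed | Expected | Expected | Expected |
| 2. P yes, S no | Expected, by the procedures limb | Unexpected, so SUSAR | Unexpected, so SUSAR |
| 3. P no, S yes, severity and outcome as listed | Meets both rows | Expected | Expected |
| 4. P no, S no | Unexpected | Unexpected, so SUSAR | Unexpected, so SUSAR |
| 5. S yes, but more severe than listed or with a different outcome | No severity or outcome test; can be read as expected by the SmPC limb (if P is no, the Unexpected row is met as well) | No severity or outcome test; can be read as expected | Unexpected, so SUSAR |

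The rules agree only in cases 1 and 4.

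- **Case 2 is a direct contradiction.** Table 5 makes the event expected, while the next sentence and Table 3 make it a SUSAR.
- **Case 3 is a contradiction inside Table 5.** The Expected row joins two limbs by *or*, so its complement would have to deny both. The Unexpected row denies only the procedures limb. Here the error could also run the other way, towards expediting a listed reaction.
- **Case 5 is a gap.** Table 5 does not say that a reaction of unlisted severity is expected. It omits the test that Table 3 applies, and so does the sentence below it.

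Consequence under section 10.6: if an event of type 2 or 5 is classed as expected, the scheduled report to the regulator moves from 7 or 15 days to the next annual DSUR. At worst that is about 12 months.

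The number of such events cannot be worked out. The protocol gives no expected number of related SAEs, and the SmPC is not among the documents.

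**The case against.** The strongest reply is that the section corrects itself. The sentence right after Table 5 ties SUSAR status to the RSI, and Table 3 ties it to product information. Anyone reading the whole short section meets the right kind of test. This stands to the extent that misclassification is possible, not certain. It does not remove the conflict: Table 5 is what the assessor is told to apply, no precedence is stated, and the sentence below it does not supply Table 3's severity and outcome test.

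A second reply is that the affected group is narrow, and this stands. Reactions to venepuncture, finger-prick, swab or spirometry would ordinarily be judged unrelated to the vaccine and never reach this step. The vaccine injection itself is the most plausible overlap between product and procedure, and without the SmPC no actual example can be shown.

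A third reply points to other safeguards. Non-exempt SAEs reach the Trial Office within 24 hours (10.4.3), the chief investigator reviews all SAEs (10.5.2), and the DMC may review any of them (10.6). Other safety issues are passed to site investigators (10.6), and urgent safety measures must be notified to the REC and MHRA within 3 days (10.7). So it would be too strong to infer that the annual DSUR is the only way such an event could come to attention. None of these steps replaces SUSAR reporting.

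A reader might also infer three wholly separate definitions. The main conflict is two-way: Table 5's procedures wording against a product-information test. The difference between Table 3 and the RSI sentence is one of detail, namely severity and outcome.

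**Conclusion.** The point holds as an internal inconsistency in a safety-reporting rule. Table 5 conflicts with the sentence below it and with Table 3, its two rows are not complements, and it lacks the severity and outcome test. A serious vaccine-related reaction that is absent from the SmPC, or more severe than listed there, could be classed as expected and reported annually instead of within 7 or 15 days.

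A reader might infer that SUSARs would inevitably be missed. The protocol does not support that, because both of its SUSAR statements rest on product information. Nor does Table 5 positively declare a reaction of unlisted severity to be expected; it leaves the matter open.

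The number of affected events cannot be derived and is likely small. The delay of about 12 months is a worst case for one event, and it assumes that Table 5 is followed over the sentence below it and Table 3. The point has no bearing on the sample size, the estimand or the primary analysis. It is worth correcting because the rule decides expedited reporting and the remedy is wording only.

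**What to change.** Reconcile Table 5 and the sentence below it with Table 3, using complementary rows:

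- Expected: nature, severity and outcome are all consistent with the approved RSI.
- Unexpected: any of the three is not consistent with the approved RSI.

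Remove trial procedures from both rows, or confine them to a separate line for events not due to the investigational product, marked as not used for the SUSAR decision.

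State which document and section form the approved RSI, and use that one term throughout. It should not be taken for granted that this is SmPC section 4.8: section 10.2 cites 4.8 for severity and causality, while section 10.5.2 refers only to an approved version of the RSI.

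The cost is a change of protocol wording and possibly a few more expedited reports.

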10.5.3 Provision of SAE follow-up information

Following reporting of an SAE for a participant, the participant should be followed up until resolution or stabilisation of the event. Follow-up information can be added to the same form the initial SAE was reported on.

10.5.4 Follow up of pregnancy outcomes for potential SAEs

Known pregnancy is an exclusion as there is a risk of congenital anomalies or birth defects in the offspring of patients as a result of their participant in the trial. Pregnancy in this patient population is possible and as such we will ask women at baseline if they are pregnant or planning to get pregnant in the next 6 weeks, which will mean they are ineligible. Woman of childbearing potential (WOCBP) will be asked to complete a pregnancy test to confirm they are not pregnant. If they are pregnant then they will be excluded from the trial.

In the unlikely event that a pregnant patient is randomised into the trial or becomes pregnant during the follow up period, this will need to be reported using the trial-specific Pregnancy Notification Form. This form will capture the pregnancy outcomes. Where the following outcomes are reported, they will also be defined as an SAE and should be reported to the STABILISE Trial Office according to the process described in Section 10.5:

- · Induced abortion (medical reason)
- · Miscarriage
- · Stillbirth

- · Birth defects
- · Neonatal unit admission
- Neonatal death

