4.2 Exclusion criteria

- Positive or indeterminate IGRA at enrolment
- Immunosuppressed in the opinion of the investigator (including, but not restricted to: Human immunodeficiency viral (HIV) infection, common variable immunodeficiency, chemotherapy, disease modifying agents for rheumatic diseases)
- Received >20mg prednisolone per day for >14 days in the last 3 months
- Known pregnancy
- Previous experience of allergic reaction to vaccine
- Unable to give informed consent

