7. TRIAL INTERVENTION

7.1 Trial intervention and dosing schedule

Participants will be randomised and those allocated to the intervention arm will receive the vaccine injection within 6 weeks from the date of randomisation. They will receive BCG vaccine (after reconstitution, 1 dose (0.1 ml) for adults contains Mycobacterium bovis BCG (Bacillus Calmette-Guerin), Danish strain 1331, live attenuated, 2-8 x 105 cfu). This is given as a one-off dose via the intradermal route of administration.

According to the manufacturer, the vaccine must be administered within 4 hours of opening the vial. Vials are only available to us in multi-dose vials, consequently batch delivery is required to avoid wastage. Sites can administer the allocated BCG to participants who gave consent in batches allowing them to make up one solution for delivery. We will be using administrating NHS hubs (organised by BCTU) where patients from 3-4 sites within the geographical area can travel to receive the BCG injection if they are within an hour travel. This will help to reduce the wastage of the vaccine. Patients will be reimbursed for the travel cost. Participants will be sent a letter for their vaccination appointment.

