9.4 Administration visit

Participants allocated to the intervention arm will receive a letter inviting them to a clinic at their closest administrative hub to receive the BCG vaccine (section 7.1). The visit and so vaccine administration to the participant, should be within 6 weeks of randomisation. The administering site will request that all women of childbearing potential (WOCBP) to arrive 10 minutes before their appointment for a pregnancy test to confirm pregnancy status. We refer to WOCBP as per Clinical Trial Facilitation Group (CTFG) guidance as "fertile, following menarche and until becoming postmenopausal unless permanently sterile. Permanent sterilisation methods include hysterectomy, bilateral salpingectomy and bilateral oophorectomy. A postmenopausal state is defined as no menses for 12 months without an alternative medical cause. A high follicle stimulating hormone (FSH) level in the postmenopausal range may be used to confirm a postmenopausal state in women not using hormonal contraception or hormonal replacement therapy (HRT). However, in the absence of 12 months of amenorrhea, confirmation with more than one FSH measurement is required."

If a woman is randomised to the BCG group and found to be pregnant after randomisation but before the administration of treatment, she will not receive the trial intervention. However, she will be followed up according to the protocol, and her data will be collected.

The administrative hub pharmacy will reconstitute the allocated IMP (section 7.2) and a delegated member of staff will administer the injection (section 7.3).

Data point to be collected:

- Pregnancy test results (where applicable)
- BCG vaccine accountability details

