9.9 Withdrawal and changes in levels of participation

Informed consent is defined as the process of learning the key facts about a clinical trial before deciding whether or not to participate. It is a continuous and dynamic process, and participants should be asked about their ongoing willingness to continue participation at all visits. Participants should be aware from the beginning that they can freely withdraw (cease to participate) from the trial at any time. A participant may wish to cease to participate in a *particular* aspect of the trial. Participants found to be ineligible post randomisation, for reasons other than to a positive or two indeterminate IGRA results, should be followed up according to all trial processes and will still have their data analysed unless they explicitly change their level of participation. Participants found to be ineligible post randomisation due to a positive or two indeterminate IGRA results will not be followed up and we will not collect any further data.

The changes in levels of participation within the trial are categorised in the following ways:

No trial intervention: The participant would no longer like to receive the trial intervention but is willing to be followed up in accordance with the schedule of assessments and if applicable using any central UK NHS bodies for long-term outcomes (i.e., the participant has agreed that data can be collected and used in the trial analysis).

No trial related follow-up: The participant does not wish to attend trial visits and/or undertake assessments in accordance with the schedule of assessments, but is willing to be followed up at standard clinic visits and if applicable using any central UK NHS bodies for long-term outcomes (i.e., the participant has agreed that data can be collected at standard clinic visits and used in the trial analysis, including data collected as part of long-term outcomes).

No further data collection: The participant is not willing to be followed up in any way for the purposes of the trial AND does not wish for any further data to be collected (i.e., only data collected prior to any changes of levels in participation can be used in the trial analysis).

The details of changes of levels in participation within trial (date, reason and category of status change) should be clearly documented in the source documents.

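### Section 10.5.4 excludes women who test pregnant, yet the only scheduled test is after randomisation, where section 9.4 keeps them in follow-up; its planned-pregnancy rule is also missing from section 4.2

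*Protocol*

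**What the plan says.** Pregnancy is handled in several places in the protocol.

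- **Section 4.2** has one relevant exclusion criterion: "Known pregnancy". The trial summary lists the same.
- **Sections 6.2 and 9.2** describe the baseline visit. Section 6.2 has women asked about existing and potential pregnancy. Section 9.2 places randomisation at this visit. Neither mentions a pregnancy test.
- **Section 9.4** places a pregnancy test at the administration visit, which only the intervention arm attends. A woman in the BCG group "found to be pregnant after randomisation but before the administration of treatment, she will not receive the trial intervention". It continues: "However, she will be followed up according to the protocol, and her data will be collected".
- **Table 2 (section 9.8)** has one entry for the pregnancy test, in the vaccine column.
- **Section 9.9** says that participants found ineligible after randomisation, other than through the IGRA result, "should be followed up according to all trial processes and will still have their data analysed", unless they choose to change their level of participation.
- **Section 10.5.4** bars women from entry on the answer to a question: "we will ask women at baseline if they are pregnant or planning to get pregnant in the next 6 weeks, which will mean they are" (the sentence ends by declaring such women not eligible). On the test it says: "Woman of childbearing potential (WOCBP) will be asked to complete a pregnancy test to confirm they are not pregnant". The stated consequence is: "If they are pregnant then they will be excluded from the trial". Its second paragraph requires a notification form if a pregnant woman is randomised or a participant becomes pregnant during follow-up.
- **Section 14.2** sets intention to treat, and **section 14.2.1** keeps BCG-arm participants who were not vaccinated under a treatment policy strategy, whatever the reason.
- **Section 7.1** sets the dosing window: "those allocated to the intervention arm will receive the vaccine injection within 6 weeks from the date of randomisation".

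**The concern.** A site that obtains a positive test at the administration visit finds two instructions. Section 9.4 tells it to withhold the vaccine and carry on with follow-up. Section 10.5.4 tells it to exclude the woman from the trial. Both cannot be followed.

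The choice matters statistically because of where the test sits. Controls have no administration visit, so no control can be removed by a test done there. If sites followed section 10.5.4 at that visit, randomised participants would be lost from the BCG arm with no counterpart in the control arm. Intention to treat is meant to prevent that kind of loss.

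There is a second, separate mismatch. An eligibility rule on planned pregnancy appears only in a safety-reporting section. A site that screens against section 4.2 would not find it, so it could be applied at some sites and not at others.

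**Working it through.** There is no plan figure to reproduce here. The check sets the passages side by side and adds two short calculations.

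**1. When can a positive test occur?**

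| Time point | Pregnancy check | Arm | Source |
|---|---|---|---|
| Baseline, before randomisation | Questions only | Both | Sections 6.2, 9.2, 10.5.4 |
| Administration visit, after randomisation | Test | BCG only | Section 9.4, Table 2 |
| 1, 3 and 12 months | No scheduled test | Neither | Table 2 |

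Scheduled tests are therefore 0 at baseline, 1 in the BCG arm and 0 in the control arm. Every scheduled test comes after randomisation.

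**2. What follows a positive test?**

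| Source | Consequence |
|---|---|
| Section 9.4 | Not vaccinated; followed up; data collected |
| Section 9.9 | Followed up and analysed, if she counts as ineligible. The only exception is the IGRA result |
| Section 14.2 | Analysed in the arm to which she was randomised |
| Section 14.2.1 | Kept in the analysis as a treatment non-receiver |
| Section 10.5.4, first paragraph | Excluded from the trial |
| Section 10.5.4, second paragraph | Reported on a notification form that captures the pregnancy outcome |

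**3. Two readings of the exclusion sentence.** Section 10.5.4 names no visit.

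- *Reading A: it means the test in section 9.4.* Then it contradicts sections 9.4, 9.9, 14.2 and 14.2.1, and can remove participants from the BCG arm only.
- *Reading B: it means a test before randomisation.* Then it does not contradict section 9.4, but it relies on a test that sections 6.2 and 9.2 and Table 2 do not contain.

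The text needs correction under both.

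**4. Size under Reading A.** The planned BCG arm is 402 (section 14.1). Each exclusion would be 1/402 = 0.25% of that arm. The documents give no pregnancy rate, so the number of exclusions cannot be derived from them. As an assumed range, 1 to 4 exclusions would be 1/402 = 0.25% to 4/402 = 1.0% of the arm.

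**5. The 6-week question.** Both periods are 6 weeks = 42 days. The question runs from baseline and the dosing window from randomisation, which is at the same visit. For a dose on day *d*, the part of the question period left after the dose is 42 − *d*:

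| Dose day | Days left |
|---|---|
| 0 | 42 |
| 14 | 28 |
| 28 | 14 |
| 42 | 0 |

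The two periods end on the same day. This describes the text; it does not show an error.

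**6. Eligibility lists.** Planned pregnancy within 6 weeks is disqualifying in section 10.5.4. It is absent from section 4.2, from the summary criteria and from the population description in section 14.2.1.

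**The case against.** The strongest answer is Reading B. In section 10.5.4 the test sentence comes straight after the question asked at baseline, and the next paragraph treats the randomisation of a pregnant patient as an unlikely exception. That order suggests that the exclusion was meant to operate before randomisation, with section 9.4 covering the period afterwards. This is a fair reading and it removes the contradiction. It does not remove the defect, because the schedule then lacks the test on which the sentence depends.

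It can also be said that the case after randomisation is already settled: sections 9.4, 9.9, 14.2 and 14.2.1 all point the same way against one loose sentence. That stands. A reader might infer that the protocol plans to exclude from one arm only, and the documents do not support this. The risk arises only if a site acts on section 10.5.4 at the administration visit.

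Two further inferences are tempting and should not be drawn.

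- *That testing only the BCG arm is itself a flaw.* Controls receive no product, so a check before dosing has no function for them. Under section 9.4 a positive test does not end follow-up, so the test alone creates no imbalance in who is analysed.
- *That the 6-week question fails because nothing is left of it after a dose on day 42.* The arithmetic is right, but nothing in the protocol says that the question must reach beyond the dose. It may have been set to cover the wait for vaccination, with the test on the day as the last check. Section 10.5.4 gives a risk to offspring as the reason for excluding known pregnancy but does not say what the 6 weeks is for. Whether time after the dose should be covered is a clinical decision, and no position is taken on it here.

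**Conclusion.** The point holds as an internal inconsistency with two parts. First, the exclusion sentence in section 10.5.4 is wrong on either reading: it contradicts the rule for the only scheduled test, or it refers to a test that is not scheduled. Second, section 10.5.4 contains an eligibility rule on planned pregnancy that section 4.2 does not list.

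The weight is low. That few participants would be affected is a judgement about a COPD population, since the protocol gives no pregnancy figure. On that judgement the effect on the primary rate ratio should be very small, and the sample size argument is untouched. What makes it worth correcting is that it bears on safety handling and on keeping randomised participants in the analysis. The conclusion assumes that Table 2 is the complete schedule of pregnancy tests.

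**What to change.** - Reconcile section 10.5.4 with sections 9.4 and 9.9 and with Table 2. State at which visit the test is done. Give a pregnancy found after randomisation one consequence for follow-up and analysis, consistent with the intention-to-treat and treatment policy text in sections 14.2 and 14.2.1.
- Reconcile sections 4.2 and 10.5.4 on planned pregnancy, so that the eligibility list and the safety section say the same. Carry the result into the summary criteria and, if it applies, the population description in section 14.2.1.
- Have the sponsor state what the 6-week period in the baseline question is meant to cover, given that it equals the dosing window.

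No clinical rule or period is proposed; those are for the sponsor to set. The cost is protocol wording, plus an entry in Table 2 if the sponsor did intend a test before randomisation. Sample size and analysis model do not change.
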